### **GOALS:**

- **Main objective**

The measurement of pain intensity according to the NRS at different times: preoperative and at the 1st, 2nd, 12th and 24th postoperative hours.

- **Secondary objectives**

Postoperative opioid consumption and comparison of total cumulative consumption between the two groups.

It will also evaluated the degree of sensory and motor block, the easy of performance of the anesthetic technique, the degree of patient satisfaction and the record of short-term complications (first 24 hours post-intervention): hematoma, pruritus, nausea and/or vomiting.

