## **JUSTIFICATION OF SAMPLE SIZE**

Because no work of this nature has been carried out previously, a sample size calculation will be not performed and all patients who underwent surgery in the 12 months that the study data collection will last were consecutively included in the study.

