## **VARIABLES EVALUATED**

The main variable will be the measurement of pain intensity according to the NRS at different times: preoperative and at the 1st, 2nd, 12th and 24th postoperative hours. As secondary variables, postoperative opioid requirements will be assessed in the form of intravenous morphine, measured in mg (only during the 2 hours of the patient's stay in the Postanesthesia Care Unit), and tramadol (mg) up to 24 hours postoperatively.

The degree of sensory block will be also assessed by a cold sensitivity test with a cotton swab dipped in cold water applied to the skin of the upper third of the arm, which will be graded with a sensitive scale going from 0 to 2 (2 being normal sensitivity to cold, 1 hypoesthesia and 0 anesthesia). The degree of motor block upon arrival at the PACU will be assessed by the movement of the arm using a simple numerical scale (0 = cannot raise the extended arm  $> 45^\circ$  and 1 = can raise the extended arm  $> 45^\circ$ ), the ease of performance of the corresponding anesthetic technique by the anesthesiologist using a simple verbal scale (easy/medium difficulty/difficult), the appearance of adverse effects (postoperative nausea and/or vomiting, hematoma, pruritus, urinary retention), the degree of patient satisfaction (very satisfied, satisfied or dissatisfied) and the notification of complications related to the anesthetic techniques performed.

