## **STATISTICAL ANALYSIS PLAN**

Continuous quantitative variables will be expressed as mean and standard deviation and the results will be contrasted using the Student's T test if normality criteria will be met, failing which they will be expressed as median and range and contrasted using the Mann Whitney's U. The qualitative variables will be expressed in absolute numbers and relative frequencies and the results of both groups will be contrasted using the Chi square. In addition, Fisher's test will be applied when necessary. Normality tests will be conducted for all continuous quantitative variables. The Kruskal-Wallis technique will be also employed with post-hoc application of the Bonferroni test for the analyses. The data will be processed using SPSS software version 19.0 (IBM Corporation, Armonk, NY, USA), assuming a p-value below 0.05 as significant.

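### NRS at 1, 2, 12 and 24 h is the main variable, but no listed test can show whether the difference between the blocks changes over time, so a pattern of significant and non-significant hours could be misread

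*Combined protocol and SAP*

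**What the plan says.** - **Main variable.** The GOALS section gives the main objective as "The measurement of pain intensity according to the NRS at different times". VARIABLES EVALUATED repeats it as the main variable: "measurement of pain intensity according to the NRS at different times: preoperative and at the 1st, 2nd, 12th and 24th postoperative hours". That is one baseline and four postoperative readings per patient. No single hour, average, change score or area under the curve is named as the primary quantity.
- **Tests for continuous variables.** The STATISTICAL ANALYSIS PLAN first gives a rule for normally distributed data: "the results will be contrasted using the Student's T test if normality criteria will be met". For all other continuous data it sets a rank-based fallback: "failing which they will be expressed as median and range and contrasted using the Mann Whitney's U".
- **A further method.** The same section adds: "The Kruskal-Wallis technique will be also employed with post-hoc application of the Bonferroni test for the analyses". Neither the factor nor the variable it applies to is stated.
- **Threshold.** "assuming a p-value below 0.05 as significant", with no distinction between hours.
- **Size.** JUSTIFICATION OF SAMPLE SIZE says "a sample size calculation will be not performed", so power at any hour is unknown.

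The plan contains no repeated-measures analysis, mixed model, group-by-time term or contrast between hours. It does not say in words how the five NRS readings are to be handled. That each hour is tested separately is an inference from the tests listed.

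**The concern.** The four postoperative readings come from the same patients, and the protocol lists them together as the main variable. With only two-sample tests available, the results will probably be a row of p-values, one per hour. A reader of such a row tends to compare its entries: significant at 1 and 2 h but not at 12 and 24 h looks like an effect that wears off. That comparison is not valid. A significant result beside a non-significant one does not show that the two effects differ; only a direct test of the difference between them can.

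This is separate from choosing a primary hour or controlling the error rate over hours. Either step would protect the individual tests. Neither would make a comparison of their p-values into evidence about the course over time.

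At stake is how the main result is interpreted. For single-injection blocks, early against late analgesia is an obvious thing to read from such a table, and the plan gives no test on which to base that reading. It also leaves the correlation between a patient's readings unused.

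**Working it through.** **The plan's own figure.** There is none to reproduce: no N, power, effect size or SD is stated.

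**What the listed tests can do.**
- Student's t and Mann-Whitney compare two independent groups on one variable, hence one hour at a time.
- Kruskal-Wallis is a one-factor test for independent samples. Applied to the two blocks, it is the same kind of comparison as Mann-Whitney. Applied across hours, it treats a patient's own readings as independent and does not involve the difference between blocks. In neither use does it test group-by-hour.
- The normality rule could also put a t test at one hour and Mann-Whitney at another, so p-values are even less comparable between hours.

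**Inputs.** From the documents: two groups, four postoperative hours, threshold 0.05 (two-sided assumed). Assumed: the same true difference at every hour, power per hour 30-80% (central value 50%), and equal correlation between hours 0.3-0.7 (central value 0.5).

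**Model.** The four test statistics are multivariate normal with common correlation ρ and common mean δ = 1.96 + Φ⁻¹(power). For 30%, 50% and 80% power, δ = 1.44, 1.96 and 2.80. An hour is significant if |Z| > 1.96. Let P₁, P₂ and P₃ be the probabilities that exactly one, two or three hours are significant.

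*Mixed pattern* (some but not all hours significant) = P₁ + P₂ + P₃. At 50% power and ρ = 0.5 each is about 0.20, giving 0.60.

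*Time-ordered pattern* (a single switch along 1, 2, 12, 24 h). The hours are exchangeable under the model, so 2 of the 4 arrangements with one significant hour are ordered, 2 of the 6 with two, and 2 of the 4 with three:

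P₁/2 + P₂/3 + P₃/2 = 0.20/2 + 0.20/3 + 0.20/2 = 0.27.

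Half of these, 0.13, run from significant to non-significant, the wearing-off direction.

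| Event under a constant effect | 50% power, ρ = 0.5 | Range (power 30-80%, ρ 0.3-0.7) |
|---|---|---|
| Some but not all hours significant | 60% | 32-72% |
| Single switch, either direction | 27% | 14-32% |
| Single switch, wearing-off direction | 13% | 7-16% |

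At ρ = 0.5 the mixed pattern falls to about 25% at 90% power and 14% at 95%.

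**Patient-level check.** Normal scores were simulated with two equal groups, the same true difference at all four hours and ρ = 0.5, in 10,000 runs per setting. Share of trials with a mixed pattern:

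| n per group | 0.4 SD | 0.5 SD | 0.8 SD |
|---|---|---|---|
| 20 | 47% | 56% | 53% |
| 30 | 55% | 60% | 32% |
| 40 | 58% | 58% | 16% |
| 60 | 59% | 44% | 3% |
| 100 | 40% | 16% | 0.1% |

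At 30 per group and 0.5 SD, power per hour is 49%, and over ρ = 0.3 to 0.7 the mixed pattern runs from 72% to 46%. With no effect at any hour, 12-18% of trials still show a mixed pattern (for four independent tests, 1 − 0.95⁴ = 18.5%).

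**The direct test on the same data.** A group-by-time test (Hotelling's T² on within-patient changes) was falsely positive in 4.4-5.5% of trials in every setting with a constant non-zero effect. A late-minus-early contrast per patient (40 per group, 0.44 SD) was falsely positive in about 5%, while the mixed pattern appeared in about 60%.

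**The case against.** **No time-course claim is announced.** The background states the aim as comparing postoperative analgesic effectiveness, and the hypotheses section mentions neither onset nor duration. Listing several hours is compatible with a plain comparison at each, for which a two-sample test is legitimate. This stands. A reader might infer that a stated time-course objective cannot be answered. The documents do not support that, because they state no such objective. The gap matters only if hours are compared with one another.

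**The 60% is not the rate of misleading wearing-off patterns.** A reader might take it so. It includes unordered patterns, such as significance at 2 h alone, which suggest neither early nor late benefit. The figures nearer to the harm are 27% for a time-ordered switch and 13% for the wearing-off direction.

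**The sizes depend on assumed power.** This also stands. With high power per hour the problem nearly vanishes: 0.1% at 100 per group and 0.8 SD. But the plan does nothing to secure high power.

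**Hour-by-hour testing is inferred, and Kruskal-Wallis is also planned.** Both are true. Kruskal-Wallis does not close the gap, because it cannot test group-by-hour in either use.

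**A mixed model may be more than is needed.** Hourly differences with 95% CIs and a sentence barring between-hour claims from p-values would remove most of the harm. That is a fair minimum, but it still leaves no test of change over time and does not use the correlation within patients.

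**Conclusion.** The concern holds in a limited form. The main variable is a repeated measure, and nothing in the analysis plan can test whether the difference between blocks changes over time. The individual hourly tests are not made invalid by this, and the documents do not commit the authors to an onset or wearing-off claim. The weakness is that the implied hour-by-hour analysis invites such a reading and offers no valid basis for it.

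If hours are compared by significance when the effect is in fact constant, a time-ordered pattern that looks like change appears in about 27% of studies, against about 5% for a direct test. These figures assume normal scores, equal correlation, the same true difference at each hour and 50% power per hour. None of these inputs comes from the documents, and the risk falls quickly above 80% power. The absence of a repeated-measures method does not depend on these assumptions.

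**What to change.** In the STATISTICAL ANALYSIS PLAN, before the outcome data are examined:

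1. Analyse NRS at 1, 2, 12 and 24 h in one repeated-measures mixed model with block group, hour (categorical), group-by-hour and preoperative NRS, allowing correlated readings within patient.
2. Report the between-group difference with 95% CI at each hour, and the group-by-hour test.
3. As a check, compute for each patient the mean NRS at 12 and 24 h minus the mean at 1 and 2 h, and compare it between groups by Mann-Whitney.
4. State that any claim that the difference changes over time rests on the interaction or this contrast, not on which hours are significant.
5. State what Kruskal-Wallis with Bonferroni is for, or remove it.

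The cost is a few lines of text and a little more analysis of readings already scheduled; no clinical procedure changes. There are two downsides. The model treats a bounded 0-10 score as continuous, which the rank-based check in step 3 helps to cover. The interaction test may have low power, particularly with an unplanned sample size, so a non-significant result must not be reported as showing a constant effect.

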## PROTOCOL

All patients will be trained preoperatively in pain assessment using a Numerical Rating Scale (NRS) from 0 (absence of pain) to 10 (maximum pain endured). All patients will receive the same anesthesia and analgesia protocol; fentanyl, propofol and rocuronium prior to intubation.

Anesthetic maintenance with 1 MAC of sevoflurane and boluses of muscle relaxant and fentanyl if there is an increase >20% in blood pressure or above baseline heart rate. The anesthetic protocol will include analgesia with 1 g of paracetamol and 50 mg of dexketoprofen every 8 hours and a bolus of 0.1 mg/kg of intravenous dexamethasone. When the patient reports an NRS > 3 and functional impact, intravenous morphine will be administered at a dose of 0.04 mg/kg every 10 minutes until NRS < 3 in the PACU and tramadol 1 mg/kg in the ward. The nursing staff and the anesthesiologist in charge of the PACU will be blind to the block received by the patient in each study group.

Before general anesthesia, patients will be assigned to one of the study groups depending on the anesthesiologist responsible for performing the blocks.

**SHAC + SSN Group (anterior approach):** with the patient in the supine position and the arm placed in abduction and slight external rotation the ultrasound probe will be positioned in the transverse axis between the coracoid process and the humeral head. After identifying the tendon of the subscapularis muscle, a puncture will be performed in a lateral to medial plane and the local anesthetic will be deposited at two levels; one deep to the subscapularis tendon at the pericapsular level of the glenohumeral joint (5 ml of ropivacaine 0.2%), and another in withdrawal at about the level of the fascia that separates the subscapularis and deltoid muscles at a more superficial level (10 ml of 0.2% ropivacaine). Subsequently, the ultrasound probe will be positioned in the transverse axis at level with the neck to locate the suprascapular nerve through an anterior approach as it ran beneath the omohyoid muscle. After hydrodissecting the correct plane with saline solution 5 ml of 0.2% ropivacaine will be administered, depositing the local anesthetic under the lower belly of the omohyoid muscle.

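### A normality test selects the NRS summary and test with no common rule across 1, 2, 12 and 24 h, and neither test uses the preoperative NRS

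*Combined protocol and SAP*

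**What the plan says.** The Variables Evaluated section defines the outcome as a set of readings, the last of them at 24 h: "The main variable will be the measurement of pain intensity according to the NRS at different times: preoperative and at the 1st, 2nd, 12th and". It names no primary time and no summary over time. The Protocol section describes the instrument as a "Numerical Rating Scale (NRS) from 0 (absence of pain) to 10 (maximum pain endured").

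The Statistical Analysis Plan section gives the default: "Continuous quantitative variables will be expressed as mean and standard deviation and the results will be contrasted using the Student's T test". The condition follows, and the alternative it leads to is a Mann-Whitney U test: "if normality criteria will be met, failing which they will be expressed as median and range and contrasted using". It adds: "Normality tests will be conducted for all continuous quantitative variables". It does not name the normality test or its threshold, or say whether the test is applied to each group or to pooled data.

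One further sentence reads: "The Kruskal-Wallis technique will be also employed with post-hoc application of the Bonferroni test for the analyses". It is tied to no variable. The significance rule is "assuming a p-value below 0.05 as significant", with sidedness not stated. No section specifies a repeated-measures model, a baseline-adjusted model, or one fixed method for NRS.

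On allocation, the Study Type section says the cohorts are not randomised. The Protocol section says a patient's group depends on which anesthesiologist performs the blocks.

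**The concern.** NRS is a bounded score, recorded here on a 0 to 10 range. Whether a sample of such scores passes a normality test depends largely on how many patients there are and how many scores pile up near zero. Neither has any bearing on which contrast answers the clinical question. Under the stated rule, that result decides both the summary and the comparison.

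The main objective is pain at several times. If the 1 h result is a median and range with a rank test and the 12 h result is a mean difference, the two cannot be set side by side as one time course of the group difference.

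A second, separate gap is that preoperative NRS is collected as part of the main variable but used by neither test. In a non-randomised comparison, the groups may start with different pain levels. Ignoring the baseline leaves that imbalance in the result and also gives up precision.

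**Working it through.** The plan states no sample size, effect size, SD or power, so it has no figure to reproduce. The text settles whether mixing can happen; simulation shows how often it might.

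**1. Can the method differ between times?** The main variable is several NRS readings. Every continuous variable is tested for normality, the result selects the method, and no sentence imposes one choice across times. So it can. The Kruskal-Wallis sentence does not remove the switch, because it is not assigned to NRS.

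**2. How often?** All inputs are assumptions: latent normal scores rounded and clipped to 0-10, SD 2.5, correlation 0.5 between times, no group difference. A t test is used if Shapiro-Wilk gives p > 0.05 in both groups, otherwise Mann-Whitney, separately at each time. A study counts as mixed when 1 to 3 of the 4 postoperative times get the t test.

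| Mean NRS at 1, 2, 12, 24 h | 20 per group | 30 | 50 | 80 |
|---|---|---|---|---|
| 5 throughout | 53% | 59% | 83% | 41% |
| 4 throughout | 61% | 78% | 71% | 3% |
| 3 throughout | 76% | 53% | 2% | 0% |
| 2 throughout | 23% | 2% | 0% | 0% |
| 2, 3, 5, 4 | 94% | 94% | 74% | 16% |

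A repeat simulation put the range at 0% to 96%. With SD 2 to 2.2 and low early, moderate later pain (means 1.5, 2, 4.5, 4), mixing was 95%, 96%, 91%, 72% and 1% at 15, 20, 30, 50 and 100 per group. Mixing is rare when pain is low throughout (from about 30 per group) or when groups are large. In both cases nearly every reading fails the test and Mann-Whitney is used throughout.

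**3. Type I error.** Across settings with SD 2 to 2.2 and 15 to 100 per group, the rate per reading was 3.6% to 6.2%, that is, near 5%.

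**4. Power.** Assumed: 40 per group, 1.2-point difference, SD 2.5, two-sided 5%, critical t about 1.991.

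- Unadjusted t test: SE = 2.5 × √(2/40) = 0.559. Ratio = 1.2 / 0.559 = 2.147. Power ≈ Φ(2.147 − 1.991) ≈ 56%.
- ANCOVA multiplies the SE by √(1 − ρ²), where ρ is the correlation with preoperative NRS.
- ρ = 0.3: SE = 0.559 × 0.954 = 0.533. Ratio = 2.250. Power ≈ Φ(0.259) ≈ 60%.
- ρ = 0.5: SE = 0.559 × 0.866 = 0.484. Ratio = 2.479. Power ≈ Φ(0.488) ≈ 69%.

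Simulation with rounded and clipped scores gives, for the plan's rule, a fixed t test and ANCOVA: 56%, 57%, 60% at ρ = 0.3, and 56%, 57%, 67% at ρ = 0.5. The simulated 67% is a little below the formula because rounding and clipping weaken the observed correlation. At ρ = 0 there is no gain. The switch itself costs about 0.5 to 2 percentage points; the rest of the gain comes from the baseline covariate.

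**The case against.** The strongest reply is that the switch does little statistical damage. It is a rule written in advance, each test keeps its error rate, and a t test fixed at all times would gain only a point or two of power. That stands. The power figures therefore support baseline adjustment, not removal of the switch, and fixing either test at all times would be enough to cure the inconsistency alone.

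A reader might also infer more than the documents support:

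- *That the plan prescribes a fresh choice at each time.* It does not say so. This is the natural reading, because the readings are listed separately and no common rule is given, but it remains an inference.
- *That pain would be measured on different scales.* The NRS stays 0 to 10 throughout; only the summary and the contrast can change.
- *That mixing is near certain.* It is likely in some scenarios and absent in others, and the documents give neither group size nor expected scores.
- *That adjusting for preoperative NRS makes the groups comparable.* It addresses baseline pain only. Confounding by anesthesiologist or hospital remains. The design is called paired, yet no matching is described, and this model would not account for pairs.

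**Conclusion.** The point holds as two limited findings.

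First, the plan allows the main variable to be summarised and contrasted differently at different times. The consequence is inconsistent reporting of the time course, not false positives or a material loss of power. Its likelihood ranges from about 0% to 96% at 20 to 80 per group under the stated assumptions, so no single percentage should be quoted.

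Second, the planned comparisons leave the preoperative NRS unused in a non-randomised study. Using it would add about 4 percentage points of power at correlation 0.3 (60 − 56) and 11 at 0.5 (67 − 56), and nothing at 0, for an assumed 40 per group and 1.2-point difference. It would also reduce bias from unequal baseline pain.

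Both are worth correcting; neither invalidates the study.

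**What to change.** In the Statistical Analysis Plan section:

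1. Stop using normality tests to select the NRS analysis.
2. Pre-specify one linear model (ANCOVA) for NRS at each of 1, 2, 12 and 24 h, with group as the factor and preoperative NRS as covariate.
3. Report the adjusted mean difference at all four times, with a 95% CI from robust standard errors or a bootstrap. Say which of the two will be used.
4. Give Mann-Whitney at all four times as a sensitivity check.
5. State which variable the Kruskal-Wallis and Bonferroni sentence serves, so that it does not leave a second route open for NRS.
6. State that the covariate handles imbalance in baseline pain only and does not remove confounding by anesthesiologist or hospital.

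The cost is analysis-plan wording: preoperative NRS is already a planned measurement, so no patients, visits or assessments are added. The downside is an adjusted mean difference on a bounded score, which the Mann-Whitney check covers.

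### Rescue opioid use reported only as median and range can read 0 versus 0 when fewer than half of each group needs the drug; add the proportion rescued and a mean difference

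*Combined protocol and SAP*

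**What the plan says.** All references are to the Combined protocol and SAP.

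- **When opioid is given (PROTOCOL).** "When the patient reports an NRS > 3 and functional impact, intravenous morphine will be administered" in the PACU; the same sentence covers the ward drug, "tramadol 1 mg/kg in the ward". The scheduled analgesia is non-opioid: "1 g of paracetamol and 50 mg of dexketoprofen every 8 hours", plus one dexamethasone bolus. No scheduled postoperative opioid is listed.
- **What is recorded (VARIABLES EVALUATED).** "postoperative opioid requirements will be assessed in the form of intravenous morphine, measured in mg", limited to the PACU stay, and tramadol in mg to 24 hours. No yes/no variable for having received rescue is listed.
- **What is to be compared (GOALS).** "Postoperative opioid consumption and comparison of total cumulative consumption between the two groups". This is the first secondary objective listed, although the plan does not rank the secondary outcomes.
- **How it is summarised (STATISTICAL ANALYSIS PLAN).** A normal continuous variable gets a mean, a standard deviation and a t test. For the others, "failing which they will be expressed as median and range" and "contrasted using the Mann Whitney's U". Counts are tied to another class of variable: "The qualitative variables will be expressed in absolute numbers and relative frequencies". No effect estimate or confidence interval is planned for any outcome.

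**The concern.** A dose given only on a trigger is exactly zero for everyone who does not meet the trigger. Its distribution is then a spike at 0 with a right tail of positive doses. Unless zeros are few, it will probably fail a normality check and fall into the median-and-range branch.

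The median says nothing about how many patients are above 0 until that number reaches half the group. The range shows whether anyone was rescued and the largest dose, but not how many were rescued. A result line could therefore show the same median and range in both groups beside a small p-value. The reader could not tell from it which block spared more patients an opioid, or by how much. The number of patients needing rescue would answer that directly. It follows from data already collected, but it is not a planned outcome.

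**Working it through.** The plan gives no rescue rate, sample size or power, so it has no figure to reproduce. The check concerns how the median behaves, with assumed rates and group sizes.

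**Step 1. When is the median 0?** Doses cannot be negative. With an even group size n, the median averages the two middle ordered values, so it is 0 exactly when at most n/2 − 1 patients received the drug. With X ~ Binomial(n, p) and p the true rescue rate:

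P(median = 0) = P(X ≤ n/2 − 1)

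P(both medians = 0) is the product over the two groups.

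**Step 2. Probability over a range of assumed rates.** For 40 per group the cut-off is 19 patients; for 60 per group it is 29.

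| Rescue rates | 40 per group | 60 per group |
|---|---|---|
| 20% vs 40% | 1.0000 × 0.8702 = 0.870 | 0.925 |
| 30% vs 45% | 0.9937 × 0.6844 = 0.680 | 0.742 |
| 30% vs 50% | 0.9937 × 0.4373 = 0.4345 | 0.448 |
| 40% vs 60% | 0.8702 × 0.0744 = 0.065 | 0.041 |
| 50% vs 70% | 0.4373 × 0.0024 = 0.001 | below 0.001 |

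Four of the five rows have the same 20-point gap. What decides the result is whether the higher rate is below half.

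**Step 3. A worked result line.** Assume 50 per group, 5 rescued in one and 20 in the other, with illustrative positive amounts of 3, 6 or 9 units.

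- Planned summary: median 0 (range 0 to 9) in both groups; Mann-Whitney p about 0.0007.
- Proportions: 5/50 = 10% and 20/50 = 40%; Fisher p about 0.001.
- Risk difference: 40 − 10 = 30 points. Standard error = √(0.4 × 0.6/50 + 0.1 × 0.9/50) = √0.0066 = 0.081. The simple 95% CI is 0.30 ± 1.96 × 0.081, about 14 to 46 points.

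**Step 4. How far the masking reaches.** With 0/50 against 24/50, a 48-point gap, both medians are still 0 (Fisher p below 0.0001). With 5/50 against 30/50, the medians are 0 and 3 units, so the masking has ended.

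**Step 5. Does the test lose power?** Simulated trials at 10% versus 40% with the same illustrative amounts gave Mann-Whitney power of 79% with 30 per group and 95% with 50. Comparing the two proportions gives 78% and 95%. Detection is essentially unchanged.

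**The case against.** The strongest reply is that this is a matter of description. The Mann-Whitney test uses every patient, zeros included, and Step 5 shows that it responds to an excess of rescued patients about as well as a test of proportions. Mean ranks, which accompany any such test, would show the direction. Median with range is a legitimate summary, and the authors could derive the rescue proportion later. Much of this stands: no inference is damaged and no data are lost. However, mean ranks are not a planned output and carry no size in mg or in patients. A proportion added after the results are seen is a post hoc choice.

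A reader might infer more than the documents support:

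- **That the medians hide a difference of any size.** They do not. Once half of a group is rescued, its median leaves 0, so the very largest contrasts are visible.
- **That a median of 0 should be expected in this study.** No rescue rate is given. The 45% in the background section concerns pain rated as intense, is not a rescue rate, and lies close to the threshold. In addition, fewer than half may receive each drug while more than half receive one or the other, so a combined total could have a non-zero median.
- **That the normality check is certain to fail.** That is likely for zero-heavy doses, but it depends on the unknown rate, the group size and the test used.
- **That the range should be replaced by the interquartile range throughout.** This would not cure the problem: with fewer than 25% rescued, the median and quartiles are all 0.

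**Conclusion.** The point holds as a reporting weakness in a secondary outcome, of minor to moderate severity. For either drug, both medians are 0 whenever fewer than half of each group receives it, even with a gap approaching 50 points. The plan then supplies a p-value without an effect size, and a summary without direction.

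The algebra is certain; whether it happens in this study is not. With 40 per group, an assumption, the chance that both medians are 0 runs from 87% (20% versus 40%) through 68% (30% versus 45%) and 43% (30% versus 50%) to 6.5% (40% versus 60%). The problem is likely only if rescue rates are below half in both groups. Above that the median becomes informative, but the proportion rescued and an effect estimate with its interval would still be missing.

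**What to change.** In VARIABLES EVALUATED, add for PACU morphine and for tramadol to 24 hours a yes/no variable: any rescue dose received.

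In STATISTICAL ANALYSIS PLAN, keep the Mann-Whitney test and add for each drug:

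1. the number and percentage of patients given any rescue dose in each group, with the risk difference and its 95% CI;
2. the between-group difference in mean mg over all patients, zeros included, with a bootstrap 95% CI.

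Quartiles may be shown beside the range as an option. Do not compare the median dose among users between groups: those patients are selected by what happened after the block, so the two subsets are not comparable.

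The cost is a change of SAP wording and one or two extra lines per opioid in the results table. It needs no new data and no change to patient care.

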## **RECRUITMENT AND RECRUITMENT OF PARTICIPANTS**

The anesthesiologist responsible for the operating room performed both the block of the anterior capsule of the shoulder and the suprascapular nerve via the anterior route and the blocks of the suprascapular and axillary nerves via the posterior route until the number of patients established in each of the groups is reached.

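### The planned tests treat patients as independent although the study group may follow the anesthesiologist; if operators mostly use one technique, the p-values are too small

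*Combined protocol and SAP*

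**What the plan says.** Two sections describe how a patient comes to receive one technique or the other. Under PROTOCOL, "patients will be assigned to one of the study groups depending on the anesthesiologist responsible for performing the blocks". Under RECRUITMENT AND RECRUITMENT OF PARTICIPANTS, "The anesthesiologist responsible for the operating room performed both the block of the anterior capsule of the shoulder" and the other technique as well, "until the number of patients established in each of the groups is reached". That number is not given, and JUSTIFICATION OF SAMPLE SIZE says that "a sample size calculation will be not performed".

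The STATISTICAL ANALYSIS PLAN compares the groups patient by patient. For continuous variables "the results will be contrasted using the Student's T test if normality criteria will be met", otherwise by Mann-Whitney. For categorical variables "the results of both groups will be contrasted using the Chi square", with Fisher's test when needed. Kruskal-Wallis with Bonferroni is added, and the threshold is "assuming a p-value below 0.05 as significant". No operator, hospital or pair term appears, although STUDY TYPE describes paired cohorts in two hospitals. VARIABLES EVALUATED does not list operator or hospital among the data to be recorded.

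**The concern.** Both techniques are ultrasound-guided and depend on the person performing them. Patients of one anesthesiologist share that person's skill and probably the hospital and surgical lists, so their NRS scores and opioid use are likely to be correlated. If each operator works mainly in one group, operator differences do not cancel between groups. They add to the variance of the group difference, and tests built on independent patients leave that part out.

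This is a variance problem and is separate from confounding. It remains when operator effects are purely random with mean zero, and adjusting for baseline pain does not remove it. At stake are the p-values for NRS, opioid use, satisfaction and ease of technique. Ease is rated by the operator, so its within-operator correlation is probably the highest.

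**Working it through.** **Inputs from the documents.** Nominal alpha is 0.05 (taken as two-sided, since the sidedness is not stated). The tests are as listed above. There is no planned sample size, power or effect size, so no design figure can be reproduced.

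**Assumptions, because the documents are silent.** 3 operators favour each technique; each treats m = 10 to 15 patients; within-operator correlation (ICC) is 0.01 to 0.10; each operator uses the favoured technique in a share s of cases.

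**Formula.** Take total variance 1 and k operators favouring each technique.

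- True variance of the group difference: 2(1 − ICC)/(km) + 2·ICC·(2s − 1)²/k.
- Variance assumed by the t test: about 2/(km).
- Ratio: D = (1 − ICC) + m·ICC·(2s − 1)². At s = 1 this is the usual design effect, 1 + (m − 1)·ICC.
- True error = 2[1 − Φ(1.96/√D)]. At D = 1 it returns 5.0%, as it should.

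**Each operator uses one technique only (s = 1).**

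| m | ICC 0.01 | ICC 0.02 | ICC 0.05 | ICC 0.10 |
|---|---|---|---|---|
| 10 | D 1.09, 6.0% | D 1.18, 7.1% | D 1.45, 10.4% | D 1.90, 15.5% |
| 15 | D 1.14, 6.6% | D 1.28, 8.3% | D 1.70, 13.3% | D 2.40, 20.6% |

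For example, at m = 15 and ICC 0.10, 1.96/√2.40 = 1.265 and 2[1 − Φ(1.265)] = 20.6%. Simulation of the t test with 3 operators per technique agrees to within about one percentage point. On a wider grid the error runs from 5.5% (m = 5, ICC 0.01) to 32.1% (m = 30, ICC 0.10).

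**Other tests.** With 3 operators per technique, m = 20 and ICC 0.05, simulated error was 16.3% for the t test, 15.1% for Mann-Whitney and 13.2% for chi-square. With 5 operators, m = 10 and the same ICC, it was 11.0%, 10.2% and 9.0%. Chi-square is affected, but less.

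**Partial preference, ICC 0.10.**

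- s = 0.9, m = 10: D = 0.90 + 10 × 0.10 × 0.64 = 1.54, error 11.4%.
- s = 0.9, m = 20: D = 0.90 + 20 × 0.10 × 0.64 = 2.18, error 18.4%.
- s = 0.7, m = 10: D = 0.90 + 10 × 0.10 × 0.16 = 1.06, error 5.7%.

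**Equal use of both techniques (s = 0.5).** D = 1 − ICC, that is 0.99 to 0.90, giving 4.9% to 3.9%. The tests are then slightly conservative.

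**Cost in power if nested.** Take a 0.8 SD effect, ICC 0.05 and a comparison of operator means.

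- 2 operators × 15 patients: SE = √[2(0.05 + 0.95/15)/2] = 0.337; 0.8/0.337 = 2.38 on 2 degrees of freedom; power about 28%.
- 3 operators × 10 patients: SE = √[2(0.05 + 0.95/10)/3] = 0.311; 0.8/0.311 = 2.57 on 4 degrees of freedom; power about 50%.

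**The case against.** The strongest objection is that the documents do not establish nesting. The recruitment section can be read as each anesthesiologist performing both techniques, and under equal use the inflation disappears. This stands, and the point must be conditional on it. It does not dispose of the point: the PROTOCOL wording points the other way, nothing in the plan requires balanced use, and a 90% preference is enough to raise the error.

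A reader might infer that the study is allocated by cluster and that its error rate is 10% to 20%. The documents do not support that. They describe no cluster allocation scheme, the word blocks in the PROTOCOL sentence means nerve blocks, and the figures needed to fix an error rate are absent. A reader might also infer that the planned confidence intervals are too narrow, but the plan specifies p-values and no confidence intervals.

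The common anesthesia and analgesia protocol, the defined fentanyl trigger and the blinded PACU staff limit some sources of correlation. They do not touch how well the block itself was placed. Systematic operator confounding, arising from the same allocation sentence, is probably the larger threat in a non-randomized comparison. That sets the priority of this point but does not answer it.

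**Conclusion.** The point holds conditionally. The allocation text is inconsistent and must be reconciled. If operators mostly use one technique, every test in the plan gives p-values that are too small. Assuming 3 operators per technique, 10 to 15 patients each and ICC 0.01 to 0.10, the t test's true error is about 6% to 21% against the nominal 5%. It is lower with partial preference and about 4% to 5% with equal use. These figures rest on the assumed cluster sizes and ICC and are not bounds. The change should be made: it is cheap, and without an operator code in the data set the problem could be neither diagnosed nor corrected in the analysis.

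**What to change.** 1. Reconcile the PROTOCOL and recruitment sections, and state how many anesthesiologists perform each technique.
2. Add a coded operator and the hospital to the recorded variables.
3. If operators perform both techniques, include operator as a stratum (fixed effect) in the NRS and opioid comparisons.
4. If operators are nested in technique, fit operator as a random effect with small-sample degrees of freedom, with hospital as a covariate where it can be estimated.
5. Base the p-value and an added 95% confidence interval on that model, and report the number of operators and patients per operator.
6. If each operator does only one technique, describe ease of technique by operator and do not test it between groups.

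The direct cost is two data fields and revised SAP wording. The statistical cost is wider intervals and, if nested with 2 to 3 operators per technique, markedly lower power, as shown above. With one operator per technique, no model separates operator from technique, and the result must be reported as descriptive with that limitation stated.
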